8.4. Secondary End Point Variables

- EQ-5D-5L: five dimensions and EQ VAS (see Appendix 2 for more details)
- IIEF15: 15 questions (see Appendix 2 for more details)
- EPIC-26: 26 questions (see Appendix 2 for more details)
- EPIC URINARY FUNCTION: 7 questions (see Appendix 2 for more details).

Imperial Clinical Trials Unit	STATISTICAL ANALYSIS PLAN: FEASIBILITY	CHRONOS
----------------------------------	--	---------

9. Statistical Methodology

9.1. Baseline Demographics

Summaries will be presented for CHRONOS-A and CHRONOS-B separately. Patient characteristics will be summarised by treatment arm. Summaries of continuous variables will be presented as means and standard deviations if approximately normally distributed, and as medians and inter-quartile ranges for skewed data; categorical variables will be presented as frequencies and percentages.

9.2. End Point Analysis Summary

End Points	Variables	Analysis	Population
End Points Primary Feasibility and acceptance of randomisation (rate per-month per-centre averaged) and compliance to allocated arm	Recorded data on whether patients have been (CONSORT): Recruited Enrolled and consented Randomised Withdrawn/Lost to follow-up In follow-up (and what stage of follow-up) Completed Days between randomisation Days between randomisation and start of treatment Days between randomisation and start of treatment Days between randomisation and start of neoadjuvant drug treatment (CHRONOS-B) Days between	Proportions of patients recruited to CHRONOS-A and CHRONOS-B Mean number of patients recruited per month per centre Recruitment rate Graph displaying recruitment rate over time Graph of actual vs target recruitment rate over time Mean number of patients randomised per month per centre Randomisation rate Graph displaying randomisation rate over time CONSORT diagram, including: Reasons for ineligibility Number who attended each visit in each arm Number of patients who received their allocated treatment/intervention Summary statistics for time between consent and randomisation by treatment arm Summary statistics for time between randomisation and treatment by treatment arm Summary statistics for time between consecutive visits Summary statistics for time between randomisation and start of neoadjuvant drug treatment (CHRONOS-B only) Summary statistics for time between start of neoadjuvant drug treatment and start of focal therapy(CHRONOS-B only)	All patients approached for enrolment and all patients randomised
	randomisation and start of neoadjuvant drug treatment (CHRONOS-B)	 (CHRONOS-B only) Summary statistics for time between start of neoadjuvant drug treatment and start of focal 	

Imperial	Clinical
Trials	Unit

STATISTICAL ANALYSIS PLAN: FEASIBILITY

CHRONOS

	1		1
	focal therapy (CHRONOS-B) Treatment details (as recorded at Visit 2/3) Protocol deviations for treatment compliance	 Treatment compliance: Proportions of patients who underwent their allocated treatment (as recorded at Visit 2/3) Drug compliance (CHRONOS-B only): Proportions of patients who returned their empty blister pack (yes/no) (as recorded at Visit 3) Proportions of patients who were given the drug and do not have a registered protocol deviation stating that they took the drug for less than 8 weeks 	
	 Reasons for ineligibility Reasons for withdrawal 	 Reasons for ineligibility Reasons for withdrawal Kaplan-Meier plots of time to withdrawal from randomisation Baseline characteristics for those who withdrew and those who completed each trial 	
	Safety analysis: AE and SAE data	 Summarise AE data by treatment arm and by site Summarise SAE data by treatment arm and by site 	All patients randomised
Secondary			
Patients' experience of each arm including systemic issues, erectile dysfunction, urinary symptoms and rectal symptoms	• EQ-5D-5L	Summarise each questionnaire by time point and by treatment arm EQ-5D-5L: Health profiles for each treatment arm at each desired time point – proportions by dimension and level Histograms of frequency EQ VAS – summary statistics for each treatment arm at each time point Histograms of frequency	All patients randomised
	IIEF15EPIC-26	IIEF15 / EPIC-26 / EPIC-URINARY DOMAIN: Summary statistics for each domain, for each time point by treatment arm	

Im	nperial Clinical Trials Unit		STATISTICAL ANA	CHRONOS		
		•	EPIC- URINARY DOMAIN			

All analyses will be repeated for CHRONOS-A and CHRONOS-B separately.

9.3. Primary End Point Analysis

The proportions of patients who opted for CHRONOS-A and CHRONOS-B will be reported.

The primary analysis of the internal pilot will calculate the mean number of patients recruited and randomised per month, per centre (including only the months in which the centre is open and recruiting). Overall recruitment and randomisation rates will also be calculated, along with their corresponding 95% confidence intervals. Recruitment rate is calculated as the number of participants recruited out of the total number approached. Randomisation rate is calculated as the number of participants randomised out of the total number recruited. Graphs displaying the recruitment and randomisation rates over time will be presented. A graph displaying the actual vs target recruitment rates will also be presented. These analyses will be conducted for CHRONOS-A and CHRONOS-B.

Compliance will be summarised using the CONSORT diagram for the internal pilot (see Section 1.1.1) which includes, the number of men who have withdrawn or been lost to follow-up (with reasons), and the number who completed each stage within each treatment arm. There will be a separate CONSORT for CHRONOS-A and CHRONOS-B.

Summary statistics for time between consent and randomisation, and randomisation and treatment will be presented by treatment arm. Summary statistics will also be presented for time between consecutive visits, by treatment arm.

For CHRONOS-B only, summary statistics will also be presented for time between randomisation and start of neoadjuvant treatment, and time between start of neoadjuvant treatment and start of focal therapy.

Treatment, for CHRONOS-A and CHRONOS-B, is recorded at Visit 2 (Treatment Visit). For focal therapy arms (CHRONOS-A (Focal arm) and CHRONOS-B) treatment is recorded by date of treatment and completed treatment details at Visit 2. For the radical arm of CHRONOS-A, treatment is recorded by date of visit 2 and completed treatment details on Radiotherapy/Brachytherapy Log and Prostatectomy Log at Visit 2. The proportions of patients in each treatment arm who underwent treatment will be presented, along with their corresponding 95% confidence intervals.

Treatment compliance will be evaluated by arm and by trial (CHRONOS-A/CHRONOS-B). Viable treatment compliance is defined as the lower end of the confidence interval for the proportion of patients who underwent treatment being $\geq 80\%$. If the lower end of the confidence interval for the proportion of patients who underwent treatment is $\geq 80\%$, then we have viable compliance to progress to the main phase. If the lower end of the confidence interval for the proportion of patients who underwent treatment is between 70% and 80%, then this indicates that remedial work is needed to improve this for the main stage. If the lower end of the confidence interval for the proportion of patients who underwent treatment is < 70%, then this could affect the primary outcome analysis and threaten the validity of the study. Data will be presented to the TSC for a final decision in this case.

Neoadjuvant drug treatment in CHRONOS-B is prescribed at randomisation. Drug compliance will be estimated using two definitions:

- Patients who returned their empty blister packs (yes/no) at Visit 3
- Patients who took the drug and did not have a registered protocol deviation stating that they
 took the drug for less than 8 weeks.

Imperial Clinical Trials Unit

For CHRONOS-B only, the proportions of patients who returned their empty blister packs (yes/no), and the proportions of patients who took the drug and did not have a registered protocol deviation, stating that they took the drug for less than 8 weeks, in each treatment arm will be reported, along with their corresponding 95% confidence intervals. Drug compliance will be evaluated by arm and by trial for each of the drug compliance definitions. Viable drug compliance is defined as the lower end of the confidence interval for the proportions being \geq 90%. If the lower end of the confidence interval for the proportions is between 80% and 90%, then this indicates that remedial work is needed to improve this for the main stage. If the lower end of the confidence interval for the proportions is < 80%, then this could affect the primary outcome analysis and threaten the validity of the study, and may require sample size re-estimation. Data for both drug compliance definitions will be presented to the TSC for a final decision in this case.

The reasons for ineligibility and withdrawal will be collected and recorded for CHRONOS-A and CHRONOS-B separately. Kaplan-Meier plots will be presented to show time from randomisation to withdrawal for CHRONOS-A and CHRONOS-B separately. Baseline characteristics will be compared between those who completed the Internal Pilot phase of the study, and those who withdrew from the Internal Pilot phase of the study.

Throughout the trial, adverse events will be recorded using the designed eCRFs. Reported adverse events (AEs) and serious adverse events (SAEs) will be listed, and then summarised, by treatment arm, in terms of severity grade (using v4.0 CTCAE grading) and causal relationship to treatment, for CHRONOS-A and B separately. Expected adverse events which are not to be reported as SAEs are listed in Appendix 1.

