To date, approximately 90% of FT cases in the UK are intermediate or low-volume high-risk cancers. There is currently no evidence comparing FT to standard of care active treatments such as radiotherapy or prostatectomy in men with clinically significant cancer. A recently completed pilot RCT comparing FT to prostatectomy (called PART) had a feasibility objective to meet a recruitment rate of 50% of men approached. However, after screening 356, 244 were eligible, of whom only 70 men accepted randomisation. 20% of those randomised to prostatectomy refused their allocation, but none declined in the FT arm. We previously reviewed 12 RCTs in which very different interventions in localised prostate cancer were compared, but failed to accrue. We proposed that there was a need to ensure novel trial designs that embrace clinical and patient equipoise (10).

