5.1. Primary Outcome Measures

Feasibility of recruitment, acceptance of randomisation and compliance to allocated arm.

- Recruitment is defined as total number of patients recruited (consented) out of the total number of patients approached.
- Randomisation is defined as the total number of patients randomised out of the total number of patients recruited (consented).
- Compliance comprises of treatment compliance (CHRONOS-A and CHRONOS-B) and drug compliance (CHRONOS-B):
 - o Treatment compliance (CHRONOS-A and CHRONOS-B):
 - Proportion of patients who underwent treatment (Focal therapy ((CHRONOS-A and CHRONOS-B)), Radiotherapy/Brachytherapy or Prostatectomy (CHRONOS-A)) as recorded by date of treatment and completed treatment details recorded at Visit 2/3 (treatment visit)
 - o Drug compliance (CHRONOS-B). This will be measured in two ways:
 - Proportion of patients who returned their empty blister pack (yes/no), as recorded at Visit 3.
 - Proportion of patients who were given the drug (recorded at Visit 2) and who did not have a registered protocol deviation (stating that the drug was taken for less than 8 weeks).

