10.3. Analysis Summary

End Points	Outcome/Variable	Analysis	Population
Feasibility and	Recorded data on	Mean number of	All randomised
acceptance of	whether patients have	patients recruited per	patients before
randomisation	been (CONSORT):	month per centre	Covid-19
(rate per-month per-centre	RecruitedEnrolled and	Recruitment rate	. All roadonsies d
averaged) and	 Enrolled and consented 	 Graph displaying recruitment rate over 	 All randomised patients during/after
compliance to	Randomised	time	Covid-19
allocated arm	Withdrawn/Lost to	Graph of actual vs	
	follow-up	target recruitment	
	 In follow-up (and 	rate over time	
	what stage of follow-		
	up)	Mean number of	
	Completed	patients randomised per month per centre	
		Randomisation rate	
		Graph displaying	
		randomisation rate	
		over time	
	Days between	Summary statistics for	
	consent and	time between consent and randomisation	
	randomisation	and randomisation	
		Reasons for ineligibility	
	Reasons for Reasons for Reasons fo	,	
	ineligibility		
	 Days between 	Summary statistics for	Patients who started
	randomisation and	time between	treatment before
	start of treatment	randomisation and treatment	Covid-19 • Patients who started
	 Days between randomisation and 	Summary statistics for	Patients who started treatment
	start of neoadjuvant	time between	during/after Covid-
	drug treatment	randomisation and start	19
	(CHRONOS-B)	of neoadjuvant	
	Days between start of	treatment (CHRONOS-	
	neoadjuvant drug treatment and start of	B only) Summary statistics for	
	focal therapy	time between start of	
	(CHRONOS-B)	neoadjuvant treatment	
	Treatment details (as	and start of focal	
	recorded at Visit 2)	therapy (CHRONOS-B	
		only)	
		Treatment compliance:	

Imperial Clinical
Trials Unit

STATISTICAL ANALYSIS PLAN: FEASIBILITY

CHRONOS

 Treatment details (as recorded at Visit 2/3) Protocol deviations for treatment compliance 	 Proportions of patients who underwent their allocated treatment (Visit 2) Drug compliance (CHRONOS-B only): Proportions of patients returned their empty blister packs (yes/no) (recorded at Visit 3) Proportions of patients who were given the drug and do not have a registered protocol deviations stating that the drug was taken for less than 8 weeks 	 Patients who started neoadjuvant drug treatment before Covid-19 (CHRONOS-B only) Patients who started neoadjuvant drug treatment during/after Covid-19 (CHRONOS-B only)

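### The SAP defines treatment compliance in two ways, and its progression rule uses the wording that, read literally, counts a man who crosses over as compliant

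*SAP*

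**What the plan says.** **Where allocation is not mentioned.** Under the SAP 5.1 heading, treatment compliance is the share of men who underwent treatment, followed by a list of focal therapy, radiotherapy or brachytherapy, and prostatectomy. The decision rule in SAP 9.3 uses the same numerator: "Viable treatment compliance is defined as the lower end of the confidence interval for the proportion of patients who underwent treatment being" 80% or more. A lower limit "between 70% and 80%, then this indicates that remedial work is needed to improve this for the main stage". Below 70%, the data go to the TSC. On the level of evaluation, 9.3 says "Treatment compliance will be evaluated by arm and by trial (CHRONOS-A/CHRONOS-B"). SAP 10.4 repeats the rule for the Covid-19 analysis. Tables 2.8 and 2.9 each have a single row for men who underwent treatment.

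**Where allocation is mentioned.** The primary outcome in SAP 5.1 is headed "Feasibility of recruitment, acceptance of randomisation and compliance to allocated arm". The analysis summary in SAP 9.2 gives treatment compliance as "Proportions of patients who underwent their allocated treatment (as recorded at Visit 2/3"), and its CONSORT entry lists "Number of patients who received their allocated treatment/intervention". SAP 10.3 has "Proportions of patients who underwent their allocated treatment (Visit 2").

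**Background.** SAP 2.1 reports of an earlier pilot RCT of focal therapy against prostatectomy that "20% of those randomised to prostatectomy refused their allocation, but none declined in the FT arm".

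**The concern.** One progression quantity has two definitions, and the rule that assigns the result to a band carries the weaker one. A man randomised to radical therapy who declines it and has focal therapy has undergone one of the treatments listed in 5.1. On the literal wording he is compliant; on the 9.2 wording he is not. No section of either document resolves his case.

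This bears on what the pilot is for. SAP 6.6 counts adherence to arm allocation among the components of feasibility, the cited earlier trial shows that refusal can be one-sided, and SAP 6.6.2 says compliance results may feed into the main-stage sample size. CHRONOS-A is a non-inferiority comparison (Protocol 1.3.1). Crossover tends to make randomised arms look alike, which favours a non-inferiority conclusion, and Protocol 8.3 names no per-protocol analysis as a check. A pilot rule that cannot register crossover would give no warning of this.

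CHRONOS-B is much less exposed. All its arms receive focal therapy, and drug compliance has a separate rule.

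**Working it through.** **Interval method.** SAP 9.3 names none. The SAP states no computed figure for this rule, but section 11 gives one interval, for 33% of 60. The Wald formula p ± 1.96·√(p(1−p)/n) gives 0.33 ± 1.96·√(0.33·0.67/60) = 0.33 ± 0.119, or 0.211 to 0.449, matching the SAP. The exact (Clopper-Pearson) interval would be 0.214 to 0.463. Since 9.3 is silent, several methods are shown below.

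**Inputs.** 30 men per arm in CHRONOS-A (SAP 6.2.3); thresholds of 80% and 70% (SAP 9.3). *Assumption:* 20% of the radical arm, 6 men, refuse and all 6 have focal therapy.

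**Radical arm, literal wording.** 30/30. Exact lower limit = 0.025^(1/30) = 88.4%. Wilson gives 88.6%; Wald degenerates to 100%. Result: viable.

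**Radical arm, allocated wording.** 24/30 = 80%. Wald: 0.80 − 1.96·√(0.80·0.20/30) = 0.80 − 0.143 = 65.7%. Wilson 62.7%, exact 61.4%. All are below 70%. Result: TSC.

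**Other numbers of crossovers, radical arm, allocated wording (95% lower limit, %).**

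| Crossovers | Count | Exact | Wilson | Wald |
|---|---|---|---|---|
| 1 | 29/30 | 82.8 | 83.3 | 90.2 |
| 2 | 28/30 | 77.9 | 78.7 | 84.4 |
| 3 | 27/30 | 73.5 | 74.4 | 79.3 |
| 4 | 26/30 | 69.3 | 70.3 | 74.5 |
| 5 | 25/30 | 65.3 | 66.4 | 70.0 |
| 6 | 24/30 | 61.4 | 62.7 | 65.7 |

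The arm misses 80% from 2 crossovers (exact, Wilson) or 3 (Wald). On the literal wording the count stays at 30/30 for every row.

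**Varying the assumption about what refusers receive.** If c of the 6 have focal therapy and the rest have nothing, the literal count is (24 + c)/30 and the allocated count stays at 24/30. With c = 0 the two wordings agree. Reading the same table, the literal result reaches the viable band at c = 5 (29/30, exact 82.8%) or c = 4 (28/30, Wald 84.4%).

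**Pooled over CHRONOS-A (n = 60, no crossover in the focal arm).** Literal: 60/60, exact lower limit 0.025^(1/60) = 94.0%. Allocated: 54/60 = 90%. Wald: 0.90 − 1.96·√(0.90·0.10/60) = 82.4%; exact 79.5%. So the pooled result on the allocated wording is viable by Wald and just short of viable by the exact method.

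**The Covid-19 repeat.** SAP 10.1 defines the population for treatment compliance by the date treatment started. Everyone in it has been treated, so the literal wording gives 100% by construction.

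**The case against.** A reader might infer that the SAP has decided to count crossover as compliance. The documents do not support that. SAP 9.2 and 10.3 both specify allocated treatment, the outcome is named as compliance to the allocated arm, and 9.3 says compliance will also be summarised through the CONSORT diagram, which counts receipt of allocated treatment. The paragraph in 9.3 just before the rule ties each arm to its own records: focal date and details for the focal arms, the radiotherapy/brachytherapy and prostatectomy logs for the radical arm. A man in the radical arm who had focal therapy would have no completed radical treatment on those logs. Crossover would probably also be visible elsewhere, since 9.2 lists protocol deviations for treatment compliance and Table 4.2 has compliance and randomisation categories.

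All of this stands as evidence of intent. It does not settle the rule. The arm-specific records support the allocated reading without stating it, and they do not cover a man who received the other arm's treatment. A deviation listing or a CONSORT count does not change the band in which the rule places the arm.

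Three limits on the consequences also stand. Low compliance leads to remedial work or TSC review, not an automatic stop, and the early-termination criterion in SAP section 11 is the recruitment rate. The non-inferiority risk belongs to the main trial, and this SAP covers only the feasibility phase. Crossover is one of several failures the pilot looks for; recruitment and acceptance of randomisation are others.

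**Conclusion.** The inconsistency is real and should be removed before the rule is applied. Taken literally, the 5.1, 9.3 and 10.4 wording contradicts the endpoint it is meant to measure. In the illustration it moves the CHRONOS-A radical arm from the top band to the bottom one, whichever interval is used for 24/30. The by-trial result is less clear-cut, because the pooled allocated figure falls on either side of 80% depending on the interval method.

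The size rests on an assumption that the documents do not supply. It would be tempting to read the cited 20% as a forecast of crossover in CHRONOS-A. That figure is refusal of prostatectomy only, and nothing is said about what those men then received. The CHRONOS-A control arm also offers radiotherapy, and men with a strong preference for focal therapy are directed to CHRONOS-B, so the rate may not carry over. Refusers who have no treatment fail under both wordings. The calculation shows that the wording can decide the band; it does not show that crossover at this level is expected.

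**What to change.** In SAP 5.1, 9.3 and 10.4 and in Tables 2.8 and 2.9, define the numerator as men who underwent the treatment they were randomised to, matching 9.2 and 10.3. For the 9.3 rule, state that the denominator is all men randomised, by arm and by trial. In the tables, add separate rows for men who received the other arm's treatment and men who received none. SAP 10.4 needs its own statement of denominator, because its population is selected on having started treatment.

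The cost is SAP wording and two table shells. Naming the interval method in 9.3 at the same time would settle the pooled result described above.

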10.1. Analysis Populations

On 05/03/2020, Covid-19 was added to Public Health England's list of notifiable diseases in England and Wales (11).

Analysis Population	Population Definition	End Points
Patients randomised	Patients randomised to the trial	Baseline demographics
before the Covid-19 pandemic	before 05/03/2020	 Recruitment rate Reasons for ineligibility
 Patients randomised during/after the Covid-19 pandemic 	Patients randomised to the trial on/after 05/03/2020	Time between consent and randomisation
 Patients who underwent radical or focal treatment before the Covid-19 pandemic 	Patients whose radical or focal treatment start date is before 05/03/2020	 Time between randomisation and treatment Treatment compliance
Patients who underwent radical or focal treatment during/after the Covid-19 pandemic	Patients whose radical or focal treatment start date is on/after 05/03/2020	(CHRONOS-A and CHRONOS-B)
Patients who started neoadjuvant drug treatment before the Covid- 19 pandemic	 Patients whose neoadjuvant drug treatment start date is before 05/03/2020 (CHRONO- B only) 	Drug compliance (CHRONOS-B)
 Patients who started neoadjuvant drug treatment during/after the Covid-19 pandemic 	Patients whose neoadjuvant drug treatment start date is on/after 05/03/2020 (CHRONOS-B only)	
Patients who underwent their most recent consecutive visits before the Covid-19 pandemic	 Patients whose most recent date of visit is before 05/03/2020 	Time between consecutive visits
 Patients who underwent their most recent consecutive visits during/after the Covid-19 pandemic 	Patients whose most recent date of visit is on/after 05/03/2020	
 Patients who attended the visit in question before Covid-19 pandemic 	Patients whose date of visit is before 05/03/2020	 Proportions of patients with missing or delayed visits
 Patients who attended the visit in question after the Covid-19 pandemic 	Patients whose date of visit is on/after 05/03/2020	
 Patients who withdrew from the trial before the Covid- 19 pandemic 	Patients whose withdrawal date if before 05/03/2020	Reasons for withdrawal
 Patients who withdrew during/after the Covid-19 pandemic 	Patients whose withdrawal date is on/after 05/03/2020	

The following analyses will only be presented is there exist patients in both the before and during/after Covid-19 pandemic populations. Analyses for populations which do not contain any patients will be omitted as they are already included in the main analysis outlined in Section 9.

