10.4. Analysis of End Points

The following analyses will be conducted separately for each of the two patient populations defined in the table above (Section 10.3).

STATISTICAL ANALYSIS PLAN: FEASIBILITY

CHRONOS

The mean number of patients recruited and randomised per month, per centre (including only the months in which the centre is open and recruiting), will be calculated. Overall recruitment and randomisation rates will also be calculated, along with their corresponding 95% confidence intervals. Recruitment rate is calculated as the number of participants recruited out of the total number approached. Randomisation rate is calculated as the number of participants randomised out of the total number recruited. Graphs displaying the recruitment and randomisation rates over time will be presented. A graph displaying the actual vs target recruitment rates will also be presented. These analyses will be conducted for CHRONOS-A and CHRONOS-B.

Compliance will be summarised using summary statistics, by treatment arm, for the time between consecutive visits, from screening visit to final follow-up visit (Visit 3 for feasibility phase). The proportions of patients, in each treatment arm, with a missing or delayed visit will also be presented. A missed visit is a visit at which no information was collected. A delayed visit is a visit which is outside of the visit window defined in the Visit Schedule (Section 6.7.2). These statistics will be presented for CHRONOS-A and CHRONOS-B.

Summary statistics for time between consent and randomisation, and randomisation and treatment will be presented by treatment arm. Summary statistics will also be presented for time between consecutive visits, by treatment arm.

For CHRONOS-B only, summary statistics will also be presented for time between randomisation and start of neoadjuvant treatment, and time between start of neoadjuvant treatment and start of focal therapy.

Treatment, for CHRONOS-A and CHRONOS-B, is recorded at Visit 2 (Treatment Visit). For focal therapy arms (CHRONOS-A (Focal arm) and CHRONOS-B) treatment is recorded by date of treatment and completed treatment details at Visit 2. For the radical arm of CHRONOS-A, treatment is recorded by date of visit 2 and completed treatment details on Radiotherapy/Brachytherapy Log and Prostatectomy Log at Visit 2. The proportions of patients in each treatment arm who underwent treatment will be presented, along with their corresponding 95% confidence intervals.

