10.8. Figures to Present

- Graph displaying recruitment rate over time (CHRONOS-A and CHRONOS-B), for patients recruited to the trial before¹ the Covid-19 pandemic
- Graph displaying recruitment rate over time (CHRONOS-A and CHRONOS-B), for patients recruited to the trial during/after² the Covid-19 pandemic
- Graph displaying actual vs target recruitment rate over time (CHRONOS-A and CHRONOS-B), for patients recruited to the trial before¹ the Covid-19 pandemic
- Graph displaying actual vs target recruitment rate over time (CHRONOS-A and CHRONOS-B), for patients recruited to the trial during/after² the Covid-19 pandemic
- Graph displaying randomisation rate over time (CHRONOS-A and CHRONOS-B), for patients recruited to the trial before¹ the Covid-19 pandemic
- Graph displaying randomisation rate over time (CHRONOS-A and CHRONOS-B), for patients recruited to the trial during/after² the Covid-19 pandemic.

¹Patients were recruited before the Covid-19 pandemic if they were recruited to the trial before 05/03/2020 (see Section 10.1)

²Patients were recruited during/after the Covid-19 pandemic if they were recruited to the trial after 05/03/2020 (see Section 10.1).

CHRONOS

11. Statistical Requirement for Early Termination of the Study

For a predicted sample size of 60 participants per trial (CHRONOS-A and CHRONOS-B), the 95% confidence interval for an estimated recruitment rate of 33% is (0.211, 0.449). Progression to the main stage will be initiated if the recruitment rate is above 21.1%.

If the recruitment rate is below 21.1%, the results of the feasibility analysis suggest that the trial is unfeasible and should be stopped. The result will be presented to the TSC, who will make the final decision, based on the evidence shown, as to whether the trial will continue to main stage. If the recruitment rate is between 21.1% and 33%, then remedial work will be implemented to improve the recruitment rate in the main stage of the trial. If the recruitment rate is greater than or equal to 33%, the trial will be deemed feasible.

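### At 20 men per drug arm the 'viable' drug-compliance grade is out of reach by exact or Wilson limits and met by Wald only at 20/20; the Covid compliance groups omit men who never started treatment

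*SAP*

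**What the plan says.** SAP 9.3 sets three bands for drug compliance in CHRONOS-B, all on the lower end of a 95% confidence interval. "Viable drug compliance is defined as the lower end of the confidence interval for the proportions being" at least 90%. A lower limit between 80 and 90% calls for remedial work. Below 80%, the result is said to threaten the validity of the study and possibly to require a new sample size. The level is double: "Drug compliance will be evaluated by arm and by trial for each of the drug compliance definitions". For the lowest band, "Data for both drug compliance definitions will be presented to the TSC for a final decision in this case". SAP 10.4 repeats these bands for the Covid subgroups.

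SAP 6.2.3 plans 20 men in each drug arm. The SAP names no interval method. It computes one interval, in section 11, for recruitment with 60 men: "the 95% confidence interval for an estimated recruitment rate of 33% is (0.211, 0.449"). Section 11 rests the stop/go rule on recruitment: "Progression to the main stage will be initiated if the recruitment rate is above 21.1"%.

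For the Covid comparison, SAP 10.1 defines the treatment-compliance groups by treatment date. The 'before' group is "Patients whose radical or focal treatment start date is before 05/03/2020"; the other group has a start date on or after that day. The drug-compliance groups are defined in the same way by drug start date. Missing or delayed visits are assessed in groups such as "Patients who attended the visit in question before Covid-19 pandemic", while 10.4 says "A missed visit is a visit at which no information was collected".

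**The concern.** A grading rule should be able to return each of its grades, and the grade should follow from how well men comply. With 20 men, a lower 95% limit lies far below the observed proportion. The by-arm grade then depends on the arm size and on an unstated interval as much as on compliance. The TSC could be told that an arm with one non-complier in 20 threatens the validity of the study, or that 20/20 is viable on the strength of an interval that claims no uncertainty.

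The Covid comparison has a different fault. Compliance asks whether randomised men received treatment, but the groups admit only men who have a start date. The men most informative about a pandemic effect, those whose treatment never took place, are removed before the proportion is formed.

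**Working it through.** **Inputs.** n = 20 per drug arm (SAP 6.2.3). By trial n = 40, because Table 2.10 has a dash for focal therapy alone. Cut-offs 90% and 80%, 95% level taken as two-sided (SAP 9.3). Assumed, not in the documents: true compliance of 95% (98% also shown), equal in both arms, men independent.

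**1. The SAP's own interval.** Wald: 0.33 ± 1.96 × √(0.33 × 0.67 / 60) = 0.33 ± 0.119 = 0.211 to 0.449. This matches section 11. For 33% of 60, the exact interval is 0.214 to 0.463 and Wilson 0.224 to 0.456; neither matches.

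**2. Lower 95% limits.** With all n men compliant:
- exact: 0.025^(1/n); for n = 20, 0.832
- Wilson: n / (n + 1.96²); for n = 20, 20 / 23.84 = 0.839
- Wald: p − 1.96 × √(p(1 − p)/n); for n = 20, 1 − 0 = 1.000, zero width

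With fewer compliant, the exact limit is the p at which P(X ≥ x) = 0.025; for Wald at 19/20, 0.95 − 1.96 × √(0.95 × 0.05 / 20) = 0.854.

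| Compliant | Exact | Wilson | Wald |
|---|---|---|---|
| 20/20 | 83.2% remedial | 83.9% remedial | 100% viable |
| 19/20 | 75.1% lowest | 76.4% lowest | 85.4% remedial |
| 18/20 | 68.3% lowest | 69.9% lowest | 76.9% lowest |

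The smallest arm in which full compliance reaches 90% is 36 men (exact) or 35 (Wilson).

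**3. Chance of each grade by arm at 95% true compliance.** P(20/20) = 0.95^20 = 0.358; P(19/20) = 20 × 0.95^19 × 0.05 = 0.377; P(18 or fewer) = 1 − 0.736 = 0.264 (unrounded terms).
- Exact or Wilson: viable 0%, remedial 36%, lowest 64%. At least one of two arms lowest: 1 − 0.358² = 0.87.
- Wald: viable 36%, remedial 38%, lowest 26%. At least one of two arms lowest: 1 − 0.736² = 0.46.

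**4. By trial, exact.** 40/40 gives 0.025^(1/40) = 91.2% (viable); 39/40 gives 86.8% and 38/40 gives 83.1% (remedial); 37/40 gives 79.6% (lowest). Chance of viable: 0.95^40 = 0.129, or 0.98^40 = 0.446. At 95%, P(39) = 0.129 × 40 × 0.05/0.95 = 0.271 and P(38) = 0.271 × 19.5 × 0.05/0.95 = 0.278. So viable 13%, remedial 55%, lowest 32%.

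**5. Covid groups.** A randomised man without a treatment start date meets neither definition in 10.1. The same is true of a drug-arm man who never started the drug. Illustration with assumed numbers, all treated as allocated: 15 men randomised before 05/03/2020 of whom 14 are treated, and 15 after of whom 9 are treated. Under 10.1 (no treatment date crossing the cut-off) these appear as 14/14 and 9/9. With all randomised men as denominator they are 14/15 (93%) and 9/15 (60%). For visits, a man who attended a visit is unlikely to have had no information collected at it, so the missed visits lie largely outside the groups in which they are counted.

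**The case against.** The arithmetic is hard to dispute; the objections concern what it shows.

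- A reader might infer that the by-arm grade is unattainable outright. The documents do not support that. The only interval the SAP computes is Wald, and by Wald 20/20 is viable; a likelihood-ratio interval also passes (90.8%). 'Unattainable' holds for exact and Wilson. What stands is that the method is unstated and that the Wald pass rests on zero width.
- A reader might infer that the bands could stop the trial. They could not by themselves. The TSC makes the decision, and the stop/go rule in section 11 is on recruitment.
- Arm and trial grades that differ are an ordinary result of 20 against 40 men and not an error in themselves.
- A reader might extend the Covid fault to the main analysis. That does not follow: section 7 keeps all randomised men, so treatment compliance in 9.3 is unaffected. Nor is Covid compliance fixed at 100%, because SAP 9.2 and 10.3 refer to the allocated treatment and 5.1 asks for completed details, so crossovers and incomplete courses may still count against it. Withdrawal reasons before and after (Tables 6.7 and 6.8) and Covid deviations (10.5) give partial evidence on uptake.
- SAP 10.1 lists recruitment rate under randomised patients. This is a labelling slip, because 10.4 and section 7 use patients approached.
- Grouping by randomisation date has its own bias: men randomised before the cut-off may have fallen due for treatment after it. This stands, and the fix has to deal with it.

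**Conclusion.** The point holds, and should be fixed before the pilot is analysed. At 20 men per drug arm, the by-arm 'viable' grade cannot be reached by an exact or Wilson interval and is reached by Wald only when every man complies. With 95% true compliance, the TSC would see at least one arm in the lowest band with probability 0.87 (exact or Wilson) or 0.46 (Wald). These figures rest on the planned arm size, a two-sided 95% level and equal, independent compliance; smaller arms make the exact and Wilson results worse. The consequence is a misleading input to the TSC, not an automatic stop.

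The Covid comparisons of treatment and drug compliance cannot show a fall in uptake, and the missed-visit comparison has the same weakness. This follows from the definitions in 10.1 and needs no assumption. Its practical size is unknown: the documents do not say how many men were randomised on each side of 05/03/2020, and section 10.1 presents these analyses only if both periods contain patients.

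**What to change.** All changes are to SAP wording.

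**SAP 9.3.** Name the exact (Clopper-Pearson) interval. State that viable drug compliance by arm is not attainable with 20 men. Apply the drug bands by trial only (n = 40), and report each arm's proportion and interval without a grade. The sponsor's lower-limit standard and cut-offs stay as they are.

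Cost: by trial, viable needs 40/40, with a 13% chance at 95% true compliance and 45% at 98%; the TSC should be told this in advance. If the exact interval also governs the treatment-compliance rule in 9.3, that rule becomes stricter than by Wald. Viable would need 20/20 in place of 19/20 in a CHRONOS-B arm, 29/30 in place of 28/30 in a CHRONOS-A arm, and 55/60 in place of 53/60 by trial. The chances at 95% true compliance are 36% against 74%, 55% against 81%, and 92% against 99%. Grading on the observed proportion instead is open to the sponsor, but should then cover treatment and drug compliance alike.

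**SAP 9.5 and section 10.**
- Use all randomised men as the denominator for Covid treatment compliance, and all men randomised to the drug arms for Covid drug compliance.
- Group drug compliance by date of randomisation, since Protocol 6.4 has the drug prescribed and dispensed within 24 hours of it.
- Group treatment compliance by date of randomisation, with a sensitivity analysis by the date treatment fell due (in the drug arms, randomisation plus the planned 84 days).
- Assess missed visits by scheduled visit date.
- In 10.4, report proportions and intervals without bands for either kind of compliance, because the subgroups are small.
- Correct the population label for recruitment rate in 10.1.

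Cost: men randomised shortly before 05/03/2020 whose treatment fell due on or after it count as 'before' in the main grouping, which can dilute a pandemic effect. In the drug arms these are men randomised from 12 December 2019 (84 days earlier). The sensitivity analysis addresses this.
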